10.4.3.2. Female Participants Who Become Pregnant

- For all Alexion products, both in development or postapproval, exposure during pregnancy must be recorded and the pregnancy followed, until the outcome of the pregnancy is known (ie, spontaneous miscarriage, elective termination, normal birth, or congenital abnormality), even if the participant discontinues the study intervention or withdraws from the study. The Investigator will collect follow-up information on the participant and the neonate and the information will be forwarded to Alexion. Generally, follow-up will not be required for longer than 3 months beyond the estimated delivery date. Any termination of pregnancy will be reported, regardless of fetal status (presence or absence of anomalies) or indication for the procedure.
- While pregnancy itself is not considered to be an AE or SAE, any pregnancy complication or elective termination of a pregnancy for medical reasons will be reported as an AE or SAE. A spontaneous abortion (occurring at < 22 weeks gestational age) or still birth (occurring at > 22 weeks gestational age) is always considered to be an SAE and will be reported as such. Any poststudy pregnancy-related SAE considered reasonably related to the study intervention by the Investigator will be reported to Alexion. While the Investigator is not obligated to actively seek this information in former study participants, he or she may learn of an SAE through spontaneous reporting.

10.5. Biomarkers

- Whole blood samples will be collected for biomarker analyses and the data will be used for research (eg, exploratory) related to ALXN1820. The samples may also be used to develop tests/assays including diagnostic tests related to ALXN1820 and/or others of this study intervention class.
- The samples may be analyzed as part of a multi-study assessment of biomarkers in the response to ALXN1820 to understand study disease or related conditions. Analyses may be done to establish normal range of values for biomarkers which may include, but are not limited to, markers of complement dysregulation (eg, Factor Ba), vascular inflammation (eg, soluble tumor necrosis factor receptors), and endothelial activation/damage (eg, soluble vascular cell adhesion molecule-1, thrombomodulin).
- The results of biomarker analyses may be reported in the clinical study report or in a separate study summary.
- Alexion or designee will store the samples obtained for biomarker analyses in a secure storage space with adequate measures to protect confidentiality.
- The samples will be retained while research on ALXN1820 continues but no longer than 25 years or other period as per local requirements.

10.6. Management of Potential Adverse Events During Study Drug Administration

Injection-associated reactions are a potential risk with the use of therapeutic protein products; these reactions can be nonimmune or immune mediated (eg, hypersensitivity reactions). Signs and symptoms may include headache, fever, facial flushing, pruritus, myalgia, nausea, chest tightness, dyspnea, vomiting, erythema, abdominal discomfort, diaphoresis, shivers, hypertension, lightheadedness, hypotension, palpitations, and somnolence. Signs and symptoms of hypersensitivity or allergic reactions may include hives, swollen face, eyelids, lips, or tongue, or trouble with breathing.

All injection-associated reactions will be reported to the Investigator and qualified designee. The Investigator and qualified designee are responsible for detecting, documenting, and recording events that meet the definition of AE or SAE and remain responsible for following up events that are serious, considered related to the study drug or study procedures, or that caused the participant to discontinue ALXN1820.

Definitions and procedures for recording, evaluating, follow-up, and reporting AEs and SAEs are outlined in Section 10.3.

Before study drug administration, the treating physician and other appropriate personnel must make certain that medication (ie, adrenaline, inhaled beta agonists, antihistamines, corticosteroids) and other equipment to treat anaphylaxis are readily available. Alexion must be notified within 24 hours of any injection site reaction requiring interruption or discontinuation of study drug. Participants who experience a reaction during the administration of study drug should be treated according to institutional guidelines.

Participants who experience a severe reaction during administration of study drug resulting in discontinuation of study drug should undergo all scheduled safety, PK, and PD evaluations required by the protocol, if possible.

10.7. COVID-19 Risk Assessment

Sickle cell disease can cause irreversible morbidity and even mortality, if untreated. As such, and due to the limited number of available treatment options, the benefit a participant may receive from joining an investigational study with a therapeutic treatment is potentially significant. Given that SCD does involve some level of immune deficiency as part of its clinical presentation and evolution, there is a theoretical concern that the risk for infection may be higher than the general population. However, there is no specific data to inform this risk further. The Principal Investigator will balance the risk/benefit considerations in their participants, taking these factors into account.

The potential risks identified and mitigation measures put in place in light of the COVID-19 pandemic are provided in Table 14.

Table 14: Potential Risks and Mitigation Measures due to COVID-19

Risks category	Summary of Data/ Rationale for Risk	Mitigation Strategy
Potential risks		
Healthcare institution availability for non-COVID-19 related activities	COVID-19 may impact the workload of healthcare institutions globally and may reduce staff availability to perform non-urgent activities and non-COVID-19 related activities.	During the time that the COVID-19 pandemic is active, Alexion will not open study sites or enroll new participants at sites unless they have the resourcing and capabilities to implement the study as per protocol.
Data quality and integrity	
Lack of availability of site personnel to perform study assessments and capture study-specific data in a timely manner and to maintain adequate quality standards.
 
Lack of availability of site personnel to ensure adequate and continuous chain of custody, storage conditions, and monitoring for investigational product and biological samples.
 
Inability of study monitors and quality personnel to conduct in-person visits to exercise adequate oversight of study execution at investigational sites.
 
Missing data (COVID-19 pandemic may impact study visit schedules, and increase missed visits and/or participant study discontinuations inadvertently resulting in missing data [eg, for protocol-specified procedures]).
	
During the time that the COVID-19 pandemic is active, Alexion will only open study sites that report enough personnel capacity to sufficiently conduct clinical study-related activities.
 
During this timeframe, site capacity will be reviewed by the site Investigator and the study Medical Monitor prior to Screening. Each site is also evaluated for the capacity to perform remote monitoring visits and remote source data verification.
 
During the time that the COVID-19 pandemic is active, it will be important to capture specific information in the eCRF that explains the reason the data are missing (eg, missed study visits or participant study discontinuations due to COVID-19).

Abbreviations: COVID-19 = coronavirus disease 2019; eCRF = electronic case report form.

10.8. COVID-19 Vaccine Risk Assessment

Following a review of the available COVID-19 vaccine data (eg, Pfizer/BioNTech, Moderna, AstraZeneca, Johnson & Johnson), it is unlikely that the immune response to a COVID-19 vaccine (and therefore the efficacy of the vaccination) would be diminished with concomitant ALXN1820 administration, based on ALXN1820's mechanism of action. There is currently no information available evaluating the safety and efficacy of COVID-19 vaccines in participants treated with ALXN1820.

Local and national guidelines should be consulted for recommendations related to COVID-19 vaccination. Alexion suggests that participants complete vaccination series before study participation, if feasible.

The potential risks identified and mitigation measures put in place in light of the COVID-19 vaccination rollout are provided in Table 15.

Table 15: Potential Risks and Mitigation Measures due to COVID-19 Vaccine

Risks Category	Summary of Data/Rationale for Risk	Mitigation Strategy
Potential risks		
Data quality and integrity	Missing data due to appointments for COVID-19 vaccination or side effects of COVID-19 vaccine may impact study visit schedules, and increase missed visits and/or participant study discontinuations, inadvertently resulting in missing data (eg, for protocol-specified procedures).	Capture specific information in the eCRF that explains the reason for missing data (eg, missed study visits due to appointments for COVID-19 vaccination or side effects of COVID-19 vaccine).

Abbreviations: COVID-19 = coronavirus disease 2019; eCRF = electronic case report form.

10.9. Abbreviations

Table 16: Abbreviations and Specialist Terms

Abbreviation or Term	Explanation
ADA	antidrug antibody
AE	adverse event
AP	alternative pathway
AUC ₀₋₁₆₈	area under the concentration-time curve from time 0 to 168 hours
Ba	complement component Ba
BMI	body mass index
C3	complement component C3
C3a	complement component C3a
C5	complement component 5
C9	complement component 9
CAP	complement alternative pathway
CFR	Code of Federal Regulations
CIOMS	Council for International Organizations of Medical Sciences
C _{max}	maximum observed serum concentration
COVID-19	coronavirus disease 2019
CTCAE	Common Terminology Criteria for Adverse Events
% CV	coefficient of variation
DMC	Data Monitoring Committee
EC	ethics committee
ECG	electrocardiogram
eCRF	electronic case report form
EDC	electronic data capture
EOS	end of study
FIH	first-in-human
FSH	follicle-stimulating hormone
GCP	Good Clinical Practice
GDS	Global Drug Safety
GDPR	General Data Protection Regulation
GLP	Good Laboratory Practice

Table 16: Abbreviations and Specialist Terms

Abbreviation or Term	Explanation
HBc	hepatitis B core
HbS	sickle hemoglobin
HbsAg	hepatitis B surface antigen
HCV	hepatitis C virus
HiB	Haemophilus influenzae type b
HIPAA	Health Insurance Portability and Accountability Act
HIV	human immunodeficiency virus
HRT	hormonal replacement therapy
IB	Investigator's Brochure
ICF	informed consent form
ICH	International Council for Harmonisation of Technical Requirements for Pharmaceuticals for Human Use
IEC	Independent Ethics Committee
IRB	Institutional Review Board
IV	intravenous(ly)
K _D	dissociation constant
LDH	lactate dehydrogenase
mAb	monoclonal antibody
MCV4	tetravalent meningococcal conjugate vaccine
NOAEL	no observed adverse effect level
PD	pharmacodynamic(s)
PK	pharmacokinetic(s)
QTcF	QT interval corrected using the Fridericia's formula
Q2W	once every 2 weeks
Q4W	once every four weeks
QW	once weekly
RBC	red blood cell
SAE	serious adverse event
SAP	statistical analysis plan
SC	subcutaneous(ly)
sC5b9	soluble complement component C5b-9

Table 16: Abbreviations and Specialist Terms

Abbreviation or Term	Explanation
SCD	sickle cell disease
SoA	schedule of activities
SOC	System Organ Class
TCR	tissue cross reactivity
TEAE	treatment-emergent adverse event
VHH	single variable domain on a heavy chain antibody
VOC	vaso-occlusive crisis
WOCBP	woman of childbearing potential

10.10. Protocol Amendment History

The protocol amendment summary of changes table for the current amendment is located directly before the Table of Contents.

DOCUMENT HISTORY	
Document/Type of Amendment (Global or Country-specific)/Date	Summary of Key Changes in the Amendment
Amendment 1.0 Global [22 August 2022]	The main rationale for this amendment is to clarify stopping rules and inclusion/exclusion criteria
Original protocol [13 May 2022]	Not applicable



Alexion Pharmaceuticals, Inc.

12 April 2023

Protocol: ALXN1820-SCD-201 Protocol Amendment 1 (22 August 2022)

Protocol Title: A Phase 2a, Randomized, Open-Label Study to Evaluate Multiple Dosing Regimens of Subcutaneous ALXN1820 in Adult Patients with Sickle Cell Disease

Protocol Administrative Change Letter #2

Reason for Letter: Clarify guidelines on determining whether a hospitalization or prolongation of a hospitalization are considered an AE/SAE. Clarify the timeframe between the (2) Screening Blood Biomarker sample collections. Clarify that randomization can be performed as early as one (1) business day prior to Day 1 dosing and clarify the position a patient must be in for blood pressure assessments.

To those sites participating in the above named and numbered clinical study, this letter serves to inform you about the following administrative changes to the above referenced protocol version.

Protocol Sections below should include additional text noted in **bold & underlined** and remove the text noted; highlighted in gray and in ~~struckthrough~~:

1. Protocol Section 9.4.2: Exploratory Assessment of VOC:

~~Complicated~~ VOCs (**uncomplicated & complicated**) that are considered exacerbated (**increased in frequency or severity**) from baseline (**Day 1**) are also to be reported as AEs.

2. Protocol Section 10.3.2: Definition of SAE:

3. Requires inpatient hospitalization or prolongation of existing hospitalization

~~In general, hospitalization signifies that~~ **Inpatient hospitalization is defined as** the participant has been ~~detained~~ **admitted** for (usually involving at least an overnight stay) **at least 24 hours**, at the hospital or emergency ward for observation and/or treatment that ~~would not have been appropriate in the physician's office or outpatient setting.~~

Complications that occur during hospitalization are AEs. If a complication prolongs hospitalization or fulfills any other serious criteria, the event is serious. When in doubt as to whether "hospitalization" occurred or was necessary, the AE should be considered serious.

Hospitalization for elective treatment of a pre-existing condition that did not worsen from baseline is not considered an AE.

3. Schedule of Activities: Tables 3, 4, and 7 footnotes:

- Blood samples for biomarkers will be collected two times prior to receiving the first dose (collect once during Screening and then again on Day 1 pre-dose, the 2

collections ~~should~~ **must** be at least ~~2~~ **1** weeks apart). Collection of blood (for serum, citrated and K2-EDTA, or P100 plasma) and urine.

4. Schedule of Activities: Tables 3, 4, and 7 footnotes:

° Randomization will occur following confirmation of all eligibility requirements.

Randomization can be performed up to 1 business day prior to Day 1 dosing.

5. 8.2.2. Vital Signs

Vital sign measurements will be taken after the participant has been resting in the supine or semi-recumbent position **or preferred position per site standard practice** for at least 5 minutes and will include temperature (tympanic or oral), respiratory rate, ~~supine~~ blood pressure, and pulse. Ideally, the same arm for each participant should be used for BP and pulse measurements. Orthostatic (standing) blood pressure will only be measured at Screening.

6. Schedule of Activities: All Tables footnotes

- At Screening, supine and standing (orthostatic) blood pressures will be performed. **At all other visits blood pressure can be performed supine or preferred position per site standard practice.**

7. Schedule of Activities: All Tables footnotes

- If a VOC occurs, samples will be collected as per unscheduled visit, **when feasible.**

Please file this letter and any IRB/EC correspondence with all copies of the protocol in the Investigator Site File and in all pertinent repositories in which the protocol is maintained.

If there are any questions concerning these changes, please contact us. These changes will also be captured in any future protocol amendment.

[REDACTED]
[REDACTED], Clinical Development Sciences
Alexion Pharmaceuticals
Phone: [REDACTED]
Email: [REDACTED]

Cc: eTMF

[REDACTED], Clinical Project Lead

Alexion Pharmaceuticals, Inc.

14 July 2023

Protocol: ALXN1820-SCD-201 Protocol Amendment 1 (22 August 2022)**Protocol Title:** A Phase 2a, Randomized, Open-Label Study to Evaluate Multiple Dosing Regimens of Subcutaneous ALXN1820 in Adult Patients with Sickle Cell Disease**Protocol Administrative Change Letter #3****Reason for Letter:** Clarify the Safety Follow-up period and intended visit sequence upon a participant meeting criteria (or deciding to) discontinue study drug intervention.

To those sites participating in the above named and numbered clinical study, this letter serves to inform you about the following administrative changes to the above referenced protocol version.

Protocol Sections below should include additional text noted in **bold & underlined**:

1. Section 7.1. Discontinuation of Study Drug Intervention

In rare instances, it may be necessary for a participant to permanently discontinue (definitive discontinuation) the study intervention. If the study intervention is definitively discontinued, the participant should remain in the study to be evaluated for safety follow-up. **The safety follow-up period should follow the periodicity and assessments defined in the SOA Table 6 from Day 99 through Day 211 and includes any subsequent Complement Activity Follow-up visits. (Cohorts 1 & 2). The safety follow-up period for the optional cohort (Cohort 3) should follow the periodicity and assessments defined in the SOA Table 8 from Day 57 through Day 169 and includes any subsequent Complement Activity Follow-up visits. The first safety follow-up visit, Day 99 for Cohorts 1 & 2 and Day 57 for Cohort 3, must occur 14 days (+/- 3 days) after the patient receives their last dose of ALXN1820.** See the SoA for data to be collected at the time of discontinuation of study intervention and follow-up and for any further evaluations that need to be completed (Section 1.3).

Please file this letter and any IRB/EC correspondence with all copies of the protocol in the Investigator Site File and in all pertinent repositories in which the protocol is maintained.

If there are any questions concerning these changes, please contact us. These changes will also be captured in any future protocol amendment.

[REDACTED], Clinical Development Sciences

Alexion Pharmaceuticals

Phone: [REDACTED]

Email: [REDACTED]

Cc: eTMF

[REDACTED], Clinical Project Lead

Alexion Pharmaceuticals, Inc.

14 August 2023

Protocol: ALXN1820-SCD-201 Protocol Amendment 1 (22 August 2022)**Protocol Title:** A Phase 2a, Randomized, Open-Label Study to Evaluate Multiple Dosing Regimens of Subcutaneous ALXN1820 in Adult Patients with Sickle Cell Disease**Protocol Administrative Change Letter #4****Reason for Letter:** Clarify the allowed use of medicines and therapy permitted during the study and provide clarification regarding bilateral tubal ligation as a method of highly effective contraception but not a permanent sterilization method (ie, women who have undergone tubal ligation will be considered of childbearing potential) and remove duplicative text for clarification.

To those sites participating in the above named and numbered clinical study, this letter serves to inform you about the following administrative changes to the above referenced protocol version.

The Protocol Sections below should include additional text noted in **bold & underlined** and remove the text noted; highlighted in gray and in ~~strikethrough~~:

1. Section 6.5.1 Allowed Medicine and Therapy

Multivitamins, contraceptives, and paracetamol (~~ie, acetaminophen, at doses of ≤ 2 g/day~~) are permitted for use during the study at the Investigator's discretion. Topical skin products should not be administered at the site of study drug injection from 24 hours prior until 24 hours following study drug administration.

2. Section 10.4.1 Women in the Following Categories Are Not Considered WOCBP

1. Premenarchal
2. Premenopausal female with one of the following:
 - Documented hysterectomy
 - Documented ~~bilateral tubal ligation or~~ bilateral salpingectomy
 - Documented bilateral oophorectomy

3. Section 10.4.2.1 Guidance for Female Participants

~~A highly effective method of contraception, including at least 1 of the following must be used until 6 months after the final dose of ALXN1820.~~

- ~~1. Intrauterine device in place for at least 6 weeks prior to first dose of ALXN1820.~~
- ~~2. Intrauterine progestogen releasing system for at least 6 weeks prior to first dose of ALXN1820.~~
- ~~3. Bilateral tubal occlusion for at least 6 weeks prior to first dose of ALXN1820.~~
- ~~4. Progestogen only hormonal contraception associated with inhibition of ovulation (implantable only) for at least 6 weeks prior to first dose of ALXN1820.~~
- ~~5. Surgical sterilization of the male partner (medical assessment of azoospermia is required if vasectomy was performed within 6 months prior to first dose of ALXN1820). Male partner is still required to use condom during heterosexual intercourse.~~

~~Female participants must not donate ova from the Day 1 Visit at least until 6 months after their final dose of ALXN1820~~

4. Schedule of Activities: All Tables footnotes

- If a VOC occurs, samples will be collected as per unscheduled visit, **within 7 days of VOC resolution** when feasible.

Please file this letter and any IRB/EC correspondence with all copies of the protocol in the Investigator Site File and in all pertinent repositories in which the protocol is maintained.

If there are any questions concerning these changes, please contact us. These changes will also be captured in any future protocol amendment.

[Redacted]

[Redacted], Clinical Development Sciences
Alexion Pharmaceuticals
Phone: [Redacted]
Email: [Redacted]

Cc: eTMF
[Redacted], Clinical Project Lead

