8.3.1. Time Period and Frequency for Collecting AE and SAE Information

All AEs and SAEs will be collected from the signing of the ICF until the last follow-up visit.

All SAEs will be recorded and reported to Alexion or the designee immediately and under no circumstance should this exceed 24 hours, as indicated in Section 10.3. The Investigator will submit any updated SAE data to Alexion within 24 hours of the date the investigational site became aware of the event.

Investigators are not obligated to actively seek AE or SAE data after conclusion of the study participation. However, if the Investigator learns of any SAE, including a death, at any time after a participant has been discharged from the study, and he/she considers the event to be reasonably related to the study intervention or study participation, the Investigator must promptly notify Alexion.

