9.4.2. Exploratory Assessment of VOC

Sickle cell disease–related pain crises (VOC) are defined as acute episodes of pain, with no medically determined cause other than a VOC event that result in a medical facility visit and treatment with either oral or parenteral narcotic agents, or with a parenteral nonsteroidal anti-inflammatory drug. Uncomplicated VOCs are defined as no occurrence of any other SCD complication during the VOC episode. Complicated VOCs are defined as the presence of a diagnosis of other SCD complications during the VOC episode. Acute chest syndrome, hepatic sequestration, splenic sequestration, and priapism are considered as VOC events in this study. Complicated VOCs are also to be reported as AEs.

The following may also be assessed if available:

- Number of VOCs leading to a healthcare visit

- Number of uncomplicated VOCs, acute chest syndrome, hepatic sequestration, splenic sequestration, and priapism
- Time to first VOC after first dose of study drug

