10.3.1. Definition of AE

AE Definition

- An AE is any untoward medical occurrence in a participant or clinical investigation participant administered a pharmaceutical product and which does not necessarily have to have a causal relationship with this treatment (ICH E2A).
- **Note:** An AE can therefore be any unfavorable and unintended sign (including an abnormal laboratory finding), symptom, or disease [new or exacerbated] temporally associated with the use of the study intervention, whether or not considered related to the study intervention.

Events Meeting the AE Definition

- Any abnormal laboratory test results (hematology, clinical chemistry, or urinalysis) or other safety assessments (eg, ECG, radiological scans, vital signs measurements), including those that worsen from baseline, considered clinically significant in the medical and scientific judgment of the Investigator (ie, not related to progression of underlying disease).
- Exacerbation of a chronic or intermittent pre-existing condition including either an increase in frequency and/or intensity of the condition.
- New conditions detected or diagnosed after study intervention administration even though it may have been present before the start of the study.
- Signs, symptoms, or the clinical sequelae of a suspected drug-drug interaction.
- Signs, symptoms, or the clinical sequelae of a suspected overdose of either study intervention or a concomitant medication. Overdose per se will not be reported as an AE/SAE unless it is an intentional overdose taken with possible suicidal/self-harming intent. Such overdoses should be reported regardless of sequelae.

Events Not Meeting the AE Definition

- Medical or surgical procedure (eg, endoscopy, appendectomy): The condition that leads to the procedure is the AE. Situations in which an untoward medical occurrence did not occur (eg, hospitalization for elective surgery if planned before the signing the ICF, admissions for social reasons or for convenience).
- Anticipated day-to-day fluctuations of pre-existing disease(s) or condition(s) present or detected at the start of the study that do not worsen.
- A medication error (including intentional misuse, abuse, and overdose of the product) or use other than what is defined in the protocol is not considered an AE unless there is an untoward medical occurrence as a result of a medication error.

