10.3.2. Definition of SAE

If an event is not an AE per definition above, then it cannot be an SAE even if serious conditions are met (eg, hospitalization for signs/symptoms of the disease under study, death due to progression of disease).

An SAE is defined as any untoward medical occurrence that, at any dose:
--

1. Results in death

2. Is life-threatening

The term “life-threatening” in the definition of “serious” refers to an event in which the participant was at risk of death at the time of the event. It does not refer to an event, which hypothetically might have caused death, if it was more severe.

3. Requires inpatient hospitalization or prolongation of existing hospitalization
--

In general, hospitalization signifies that the participant has been detained (usually involving at least an overnight stay) at the hospital or emergency ward for observation and/or treatment that would not have been appropriate in the physician’s office or outpatient setting. Complications that occur during hospitalization are AEs. If a complication prolongs hospitalization or fulfills any other serious criteria, the event is serious. When in doubt as to whether “hospitalization” occurred or was necessary, the AE should be considered serious.
--

Hospitalization for elective treatment of a pre-existing condition that did not worsen from baseline is not considered an AE.

4. Results in persistent disability/incapacity

- | |
|--|
| 
• The term disability means a substantial disruption of a person’s ability to conduct normal life functions.• This definition is not intended to include experiences of relatively minor medical significance such as uncomplicated headache, nausea, vomiting, diarrhea, influenza, and accidental trauma (eg, sprained ankle) which may interfere with or prevent everyday life functions but do not constitute a substantial disruption. |
|--|

5. Is a congenital anomaly/birth defect
--

6. Other situations:

- | |
|--|

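### Does judging VOC exacerbation against Day 1 leave the AE and SAE status of VOCs unworkable?

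*Protocol*

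**What the plan says.** Letter #2, item 1, replaces the AE sentence of Protocol Section 9.4.2. VOCs, uncomplicated and complicated, "that are considered exacerbated (increased in frequency or severity) from baseline (Day 1) are also to be reported as AEs". Letters #3 and #4 leave this alone. Section 9.4.2 still states: "Acute chest syndrome, hepatic sequestration, splenic sequestration, and priapism are considered as VOC events in this study".

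Other rules bear on the same events:

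- Letter #2, item 2 (Section 10.3.2) keeps the sentence "Complications that occur during hospitalization are AEs" and treats the event as serious if a complication prolongs the stay.
- Section 10.3.1 counts as AEs "Exacerbation of a chronic or intermittent pre-existing condition including either an increase in frequency and/or intensity of the condition" and "New conditions detected or diagnosed after study intervention administration even though it may have been present before the start of the study". It excludes expected daily variation in conditions "present or detected at the start of the study that do not worsen".
- Section 10.3.2 opens: "If an event is not an AE per definition above, then it cannot be an SAE even if serious conditions are met".
- Section 8.3.1: "All AEs and SAEs will be collected from the signing of the ICF until the last follow-up visit".

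The SAP carries an exacerbation flag in the AE listing (4.2.1) and in the VOC listing (4.4), where a yes leads to an AE record. Neither section defines the flag. SAP 4.1 takes baseline as the last non-missing value before the first dose.

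**The concern.** Frequency needs a period, and Day 1 is not one. Severity on Day 1 exists only if a crisis is under way. Read literally, the Day 1 count is zero for almost everyone, so any later VOC is an increase. The SAP's baseline definition supplies no period. AEs are collected from consent, so a VOC during Screening comes before the reference it would be judged against.

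The rules also seem able to disagree. Suppose acute chest syndrome arises during a VOC admission and prolongs it, while the patient's VOC pattern is judged no worse. If item 1 were the only route, this would not be an AE and so could not be an SAE. The complications sentence makes it both. Incidence of TEAEs and SAEs is part of the primary endpoint, and with two participants one reclassified SAE would be visible.

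**Working it through.** **1. Is VOC frequency missing at Day 1?** No. Inclusion criterion 6 requires 1 to 10 VOCs in the past 12 months, and eligibility is assessed at Screening and on Day 1 (schedule footnotes). The VOC diary starts after consent (8.1.5) and is reviewed on Day 1. The SAP lists 12-month and 3-month VOC counts as baseline characteristics (6.2). The letter does not name the window. The data exist.

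**2. Is item 1 exclusive?** It says exacerbated VOCs are *also* to be reported, which is a sufficient condition. The SAP 4.4 label runs in the same single direction. The opening of 10.3.2 refers back to the AE definition in 10.3.1, not to 9.4.2, so item 1 alone cannot stop an event from being an AE or SAE.

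**3. The acute chest syndrome case under each rule.**

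| Rule | Result |
|---|---|
| 9.4.2 (item 1) | No instruction, since not judged exacerbated |
| 10.3.1 | AE if newly diagnosed; daily variation is an awkward fit |
| 10.3.2 (item 2) | AE, and serious because the stay is prolonged |

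Read together, these give an AE and an SAE. The tension between items 1 and 2 would be the same under any baseline.

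**4. How much does the reference matter?** The documents give no figure, so this is an illustration. It assumes Poisson counts and an unchanged rate r of 1, 4 or 10 per year, within the entry range. The mean is m = r × days / 365.25. The periods are the 84-day Treatment Period and 184 days (84 days to the Day 85 dose, plus the 100 days of the SAP 6.1 TEAE window).

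- Literal Day 1 (zero): P(N ≥ 1) = 1 − exp(−m).
- 12-month history scaled to equal time: P(N > m), counting any excess as an increase.

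| | r = 1 | r = 4 | r = 10 |
|---|---|---|---|
| m, 84 days | 0.230 | 0.920 | 2.300 |
| Literal Day 1 | 21% | 60% | 90% |
| 12-month history | 21% | 60% | 40% |
| m, 184 days | 0.504 | 2.015 | 5.038 |
| Literal Day 1 | 40% | 87% | 99% |
| 12-month history | 40% | 33% | 39% |

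History changes nothing at 1 per year, nor at 4 per year over 84 days. Elsewhere it lowers the share but still flags 33% to 40% of unchanged patients. The choice of history matters too: at 10 per year over 84 days, the 12-month count gives 40%, a 3-month count 55% and a full 56-day Screening diary 48%.

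**5. Severity on Day 1.** The chance of a crisis in progress is 1 − exp(−r × D / 365.25). For assumed episodes of D = 3 to 10 days this is 0.8% to 2.7% at 1 per year and about 8% to 24% at 10 per year. A literal reading would leave the severity test empty for most patients, which suggests that status up to Day 1 is meant.

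**6. Scale.** Two participants who complete dosing would have 2 × r × 184 / 365.25, or about 1, 4 or 10 VOCs in total at the three rates, and fewer if stopped early.

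**The case for a change.** The best case for a change is that this is live wording feeding the primary safety listing, that a short clarification would be cheap, and that with two participants the individual listings are the result. A history reference also has some power to discriminate. If the rate doubles, it flags 63%, 77% and 94% over 184 days, against 40%, 33% and 39% when nothing changes.

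Part of this stands. No look-back period is stated, and the letter does not say how 9.4.2 fits with the complications sentence. Acute chest syndrome that is itself the presenting VOC, in a patient who has had it before, is left to judgement. The Screening point stands only in part: SAP 6.1 classes events before the first dose as pretreatment, so they cannot enter the TEAEs, though their SAE status could still be argued.

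The remedy gains little. To name the 12-month count, the 3-month count and the diary together would leave open which governs. To name one would still flag a third or more of unchanged patients over 184 days, so the investigator's judgement would decide as it does now. The SAP also places listing specifications in a separate Data Presentation Plan, so a definition of the flag may exist outside these documents.

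**Conclusion.** No change to the plan is needed. The gap is one that investigators and analysts can fill sensibly: read Day 1 as the patient's known VOC status on entering treatment, and apply 9.4.2 together with 10.3.1 and 10.3.2.

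The consequence is at most an inconsistent AE or SAE label on a few events. The study ended early with 2 participants, data are only listed (SAP 1, 1.2), and summary statistics are dropped (SAP 4.5). SAP 4.4 lists VOCs with start and end dates, complicated or uncomplicated type, complication category, pain intensity and the flag itself. A reader can set these beside the AE listing by hand, as ordinary data review would do, and see any hospitalised or complicated VOC without an AE record. Other AEs and the laboratory, vital-sign and ECG data are untouched.

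This rests on two readings of the text: *also* as non-exclusive, and the SAE condition as pointing to 10.3.1. The percentages are illustrative and depend on constant Poisson rates and on counting any excess as an increase, which no document prescribes. Had the study run to its planned size with summarised incidence, a stated window would have been worth more.
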